6.9.2 Exclusion criteria

1. Patients with primary NB in CNS.
2. Patients must not have obstructive or symptomatic communicating hydrocephalus as determined by Ommaya patency/CSF flow study.
3. Patients must not have worsening of neurologic function, according to assessment by investigator, within 3 weeks prior to first dose of ^{131}I -omburtamab.
4. Patients must not have an uncontrolled life-threatening infection.
5. Patients must not have received cranial or spinal irradiation less than 3 weeks prior to first dose of ^{131}I -omburtamab in this trial.
6. Patients must not have received systemic chemo/ immunotherapy (corticosteroids not included) less than 3 weeks prior to enrollment in this trial.
7. Patients must not have received any anti-B7-H3 treatment prior to enrollment in this trial.
8. Patients must not have severe major non-hematologic organ toxicity; specifically, any renal, cardiac, hepatic, pulmonary, and gastrointestinal system toxicity must fall below Grade 3 prior to enrollment in this trial. Patients with stable neurological deficits (due to brain tumor) are not excluded. Patients with Grade 3 or lower hearing loss are not excluded.
9. Patients must not be pregnant or breast-feeding.
10. Female patients of child-bearing potential (i.e. having experienced menarche) and male partners to female patients who do not agree to the use of effective contraception during treatment and for a period of 12 months after the last ^{131}I -omburtamab dose. Effective contraception for women is defined as intrauterine devices or hormonal contraceptives (contraceptive pills, implants, transdermal patches, hormonal vaginal devices, or injections with prolonged release). Effective contraception for male partners is defined as use of condoms. To be exempt from the requirement to use contraception after ^{131}I -omburtamab treatment, one of the criteria described in section 9.2.11 of this protocol must be met.
11. Fertile male patients who do not agree to the use of condoms during treatment and for a period of 12 months after the last ^{131}I -omburtamab dose. For a sterilized male patient to be exempt from the requirement to use contraception after ^{131}I -omburtamab treatment, he must have undergone surgical sterilization (vasectomy).

6.9.3 Treatment discontinuation criteria

A patient must be discontinued from treatment if:

- Treatment-related CTCAE Grade 3 or 4 anaphylaxis.

- CTCAE Grade 4 neurotoxicity.
- Development of obstructive or symptomatic communicating hydrocephalus
- Unexpected, IMP-related and clinically significant Grade 4 toxicity.
- Disease progression before cycle 2.
- The investigator requests discontinuation of treatment for medical or safety reasons, including lack of treatment response; or
- The patient receives prohibited therapy and/or undergoes prohibited procedures during the trial.

Diagnosis of chemical meningitis (symptoms of clinical meningitis but cultures for infective agents were negative) in which either: a) event is non-responsive to IV steroids, b) radiologic or operative intervention was indicated, or c) presence of focal neurologic deficit. A patient discontinued from treatment should as soon as possible attend the week 4 or 8 visit as applicable, and subsequently be followed at the short and long-term follow-up visits. The investigator should follow any SAE still ongoing after discontinuation until the event has been resolved or the investigator assesses the SAE as being chronic or stable.

A patient should be withdrawn from the trial if:

- The patient or legal guardian withdraws consent for any reason;

If the patient is withdrawn from the trial, the investigator should:

- Ensure the safety of the patient.
- Offer the best possible treatment outside of the trial.

Furthermore, after withdrawal for any reason, the investigator, in consultation with the patient/legal guardian, will recommend future treatment based on clinical practice at the investigational site.

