8.1.2 Secondary endpoints

1. CNS/LM PFS at 6 and 12 months will be estimated based on the time from first treatment dose to CNS/LM progression or death from any cause. Patients alive without CNS/LM progression at time of analysis, will be censored at last date of disease evaluation without evidence of progression.
2. OS at 12 months will be estimated based on the time from first treatment dose to death by any cause. Patients alive at time of analysis, will be censored at last date known to be alive.
3. ORR assessed as a combination of partial response and complete response as defined by the Response assessment in Neuro-Oncology (RANO) group criteria for brain metastasis (Lin et al, 2015) or leptomeningeal metastases as defined by EANO-ESMO criteria (Le Rhun et al, 2017). ORR will be assessed at 6 months after the first treatment dose of ^{131}I -omburtamab
4. ORR according to CSF cytology. Response is defined as a complete response when CSF converts from positive at baseline to negative after treatment with ^{131}I -omburtamab
5. Whole-body, organ, blood, and CSF radiation dosimetry.
6. Pharmacokinetic analysis of activity in blood and CSF including derivation of best-fit uptake and/or clearance parameters (half-times, maximum value) of time-activity concentration curves and of I-131 residence times (i.e., cumulated activity) concentrations (in $\mu\text{Ci}\cdot\text{h/g}$).
7. The frequency, type, and duration of treatment-emergent severe adverse events and serious adverse events, including clinically significant laboratory abnormalities. All adverse events will be graded according to Common Terminology Criteria for Adverse Events (CTCAE), version 4.0.
8. Performance assessment to monitor gross changes in neurological function is performed at week 26 and subsequently every 6 months during trial period.
9. The rate of ADA occurrence assessed three weeks after the first and second treatment dose of ^{131}I -omburtamab

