9 PROCEDURES AND ASSESSMENTS

9.1 Efficacy assessments

9.1.1 Primary endpoint

OS rate at 3 years. The time frame for assessment of OS will be from the first treatment dose of ^{131}I -omburtamab to time of death from any cause. OS will be censored at last date of contact. Survival at 3 years will be estimated by Kaplan-Meier methods.

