12.8 Sample Size

Assuming an [REDACTED]

[REDACTED]

[REDACTED]

Power was estimated by simulation using an exponential model and an assumed lost to follow-up rate of 10%.

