12.9 Handling of missing data

For the primary time to event efficacy endpoint, patients who do not have an event will be censored at their date of their last evaluation. It is unlikely that missing of safety data will occur in the targeted patient population, but in case it happens the data will not be imputed.

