Before signing the Informed Consent, the patient/parents must be given sufficient time to consider the possible participation. Further, each patient must be informed about their right to withdraw from the trial at any time. Parents and patients will also be informed that research participation is voluntary but if they withdraw from the trial, their data will still be used. When the informed consent form has been signed, the patient/parent(s) receives a copy of the signed form and the original is retained in the investigator site file. A second copy may be kept in the patient's medical notes. The informed consent forms must be signed and dated both by the signee and by the person providing the information to the patient/parents. It is recommended to notify the participant's family doctor of the participant's consent to participate in the trial.

13.4 Special considerations for patients having the Ommaya reservoir implanted at the referring hospital or locally but before entering the screening period.

The Ommaya reservoir is to be placed after the written informed consent has been obtained. In cases where placing of the Ommaya is considered in association with the surgical procedure that is recommended before enrollment in the trial, informed consent may be obtained up to three months before the start of the screening period. This is considered acceptable since placing of the Ommaya in association with the anesthesia induced for the surgical resection of the tumor will reduce the burden to the patient by avoiding an extra surgical procedure. Furthermore, the patient may receive high dose chemotherapy in the period leading up to the screening period which may be associated with myelosuppression and therefore rendering an invasive procedure like Ommaya placement not feasible.

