15 DATA HANDLING AND RECORD KEEPING

15.1 Electronic case report forms

For each patient enrolled, an eCRF must be completed and signed by the investigator. This also applies to records for those patients who fail to complete the trial. If a patient withdraws from the trial, the reason must be noted in the eCRF. If a patient is withdrawn from the trial because of a treatment-limiting AE, thorough efforts should be made to clearly document the outcome. For screening failure patients, the date of informed consent and reason for failure to enroll must be captured in the eCRF.

15.1.1 eCRF

An eCRF will be established to collect data in a validated and effective way and in compliance with ICH guidelines including audit trail and a query module. The patient's identity must always remain confidential. All information in the eCRFs should be in English.

The completed original eCRF data are the sole property of the sponsor and should not be made available in any form to third parties (except for authorized representatives of appropriate regulatory authorities) without written permission from the sponsor.

The investigator is responsible for ensuring the accuracy, completeness, legibility and timeliness of the data recorded in the eCRFs.

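### Nothing in the protocol body secures survival status after consent withdrawal, so the single-arm 3-year OS estimate is biased upward if withdrawal or loss is linked to poor prognosis

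*Combined protocol and SAP*

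**What the plan says.** Section 6.9.3 describes two exits. A child who stops treatment, for example for toxicity or for progression before cycle 2, attends the next applicable visit and must "subsequently be followed at the short and long-term follow-up visits". Withdrawal from the trial has one listed trigger: "The patient or legal guardian withdraws consent for any reason". The duties that follow are the child's safety, the best treatment available outside the trial and advice on future treatment. Survival status is not among them, and no partial withdrawal is described.

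Section 13.3 tells families that "if they withdraw from the trial, their data will still be used". Section 15.1, on the eCRF, adds: "If a patient is withdrawn from the trial because of a treatment-limiting AE, thorough efforts should be made to clearly document the outcome". Section 6.9.3 does not list an adverse event as a reason for trial withdrawal.

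For the primary endpoint, section 9.1.1 says that "OS will be censored at last date of contact" and uses Kaplan-Meier at 3 years. Section 12.9 says that "patients who do not have an event will be censored at their date of their last evaluation", and section 8.1.2 (12-month OS) says "Patients alive at time of analysis, will be censored at last date known to be alive". The visible part of section 12.8 gives "an assumed lost to follow-up rate of 10" percent as an input to the power simulation. Section 12.9 contains no sensitivity analysis for early censoring.

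**The concern.** Kaplan-Meier gives a censored child the same future risk as the children still under observation. That is reasonable when follow-up ends for reasons unrelated to prognosis. It fails if families withdraw consent, or drop out of contact, because the child is doing badly: the deaths that follow are not counted and the estimate rises.

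The primary result is one OS rate from at least 32 children in a single arm. No concurrent group carries the same error, and the 95% confidence interval does not allow for it. In the exploratory comparison in section 12.3, the controls come mainly from a registry that section 12.2 describes as continuously updated, so completeness of follow-up could differ between the two groups.

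**Working it through.** **Plan's own figure.** None can be reproduced. The assumed OS rates and the power in section 12.8 are redacted, which is not an error in the plan.

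**Inputs.** N = 32 (minimum, section 6.8). Kaplan-Meier at 36 months (section 9.1.1). Illustrative true 3-year OS of 56%, the earlier single-center figure in section 4.1; 40%, 30% and 10% are assumptions. Three departures are used because 10% of 32 is 3.2. This borrows the size of the loss-to-follow-up assumption and does not predict withdrawals.

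**Hand check, early departure.** Suppose 18 of 32 children are alive at 3 years, with complete follow-up:

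18/32 = 56.3%.

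If 3 of the 14 who die are censored before the first death, they leave the risk set:

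18/29 = 62.1%, which is +5.8 points.

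**Hand check, one child censored just before death.** With r children at risk at that time, the factor (r − 1)/r drops out of the product, so the estimate is multiplied by r/(r − 1).

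- First death (r = 32): 56.25% × 32/31 = 58.1%, +1.8 points.
- Last of the 14 deaths (r = 19): 56.25% × 19/18 = 59.4%, +3.1 points.

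One child is therefore worth roughly 2 to 3 points at this survival level.

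**Simulation.** Exponential survival, N = 32, 6,000 runs per scenario. Departing children are drawn either at random or only from those who die within 3 years. Bias in percentage points:

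| True 3-year OS | 3 lost at random | 1 leaves 1 month before death | 3 leave 1 month before death | 3 leave at a random time before death | 3 leave at the start |
|---|---|---|---|---|---|
| 56% | 0.0 | +2.3 | +7.3 | +6.6 | +5.8 |
| 30% | 0.0 | +1.6 | +5.1 | +4.1 | +3.1 |
| 10% | 0.0 | +0.8 | +2.5 | +1.6 | +1.1 |

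A separate run at 40%, with three children leaving 1 month before death, gave about +6.

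**Lower bound.** Count every child withdrawn or lost before 3 years as a death.

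- If the three departures are random, the expected figure is the true rate × 29/32: 56% becomes 51%, 40% becomes 36%, 30% becomes 27%. Kaplan-Meier is unbiased in this case, so the bound is pessimistic.
- If all three die within 3 years, the bound equals the truth: 18/32 = 56.3%, against 62.1% from Kaplan-Meier in the early-departure example.

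If all other children have complete follow-up, the bound is the number known alive at 3 years divided by N. It then does not depend on which of the three censoring wordings is applied.

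**The case against.** Much of the follow-up structure is sound, and several stronger readings fail.

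- **A reader might infer that toxicity or progression ends survival follow-up.** It does not: section 6.9.3 keeps those children in the short- and long-term visits. Nor must a family leave the trial to obtain other therapy. Section 7.3.1 allows further anti-cancer treatment after the MRI that follows the last dose, and section 7.4 covers treatment after IMP discontinuation. That families are likely to withdraw at such moments is not supported by the documents.
- **A reader might infer that sections 15.1 and 6.9.3 contradict each other.** Section 15.1 is a conditional sentence about completing the eCRF. A guardian may withdraw consent for any reason, including an adverse event, and section 10.8 refers to 6.9.3 for withdrawn patients. The two can be read together. The wording is loose, and the outcome to be documented is not identified as survival.
- **Low-burden survival collection already exists.** Section 6.3 requires it through referral hospitals for children who have returned home. This stands, but it concerns children still in follow-up.
- **Section 13.3 keeps withdrawn patients' data in use.** It does not say that new survival data will be collected.
- **The consent form or the detailed SAP may cover this.** Consent pages were removed, section 12.1 defers detail to the SAP, and sections 12.2 and 12.8 are partly redacted. The gap is therefore shown only for the protocol body. A SAP table also could not restore survival data that were never collected.
- **The error is small beside sampling error.** At 56% and N = 32 the standard error is √(0.56 × 0.44/32) = 8.8 points, about ±17 for a 95% interval. Seven points would not remove the contrast with the 8.2% historical rate in section 4.1. This limits the consequence, but the error runs in one direction and the interval does not reflect it.

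**Conclusion.** The point holds in a limited, conditional form. The protocol body does not provide for survival status after consent withdrawal, and OS is then censored at last contact. If withdrawal or loss is linked to poor prognosis, the 3-year OS estimate is too high. At N = 32 the size is about +2 points for one child leaving a month before death, and about +5 to +7 for three at true rates of 30% to 56%. Earlier departure gives somewhat less, and random loss gives nil.

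These figures rest on assumed numbers, timing and prognosis of departures. A reader might take the 10% in section 12.8 as a withdrawal forecast and +7 as the expected bias. The documents support neither: the 10% is a loss-to-follow-up input to a power simulation, and the three-child case assumes that every lost child dies within 3 years. The changes are worth making because they are cheap and bear directly on an uncontrolled primary estimate.

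**What to change.** 1. In section 6.9.3, separate stopping treatment, stopping visits and refusing further data. After withdrawal, collect vital status to 3 years through the treating or referring physician, or a registry where law allows, unless the family refuses that item. Carry the choice into the consent form.
2. Beside the main estimate, report 3-year OS with every child withdrawn or lost before 3 years counted as a death at last contact, labelled as a lower bound. State that a child seen alive at the week-156 visit within its ±4-week window (Table 1, note 21) is not lost, so that visit timing does not create deaths.
3. As a minor wording point, reconcile section 15.1 with 6.9.3 so that an adverse event alone is not read as ending survival follow-up. One OS censoring date across sections 8.1.2, 9.1.1 and 12.9 could be set in the same edit.

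The cost is a consent-form line, short wording changes and one extra table. The downside is that the lower bound will look less favourable than the main estimate whenever a child is withdrawn or lost, and will be too pessimistic if those children are in fact alive.

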7 TREATMENTS

7.1 Investigational Medicinal Product

Screening assessments will be evaluated before any patient receives IMP. The patient and/or legal guardian must have received patient information and signed the ICF. Eligible patients must meet all inclusion criteria and must not violate any of the exclusion criteria (please see sections 6.9.1 and 6.9.2).

Monoclonal antibody omburtamab is a murine IgG1 antibody that is raised in BALB/c mice and recognizes tumor associated antigen B7-H3. Omburtamab will be radiolabeled with iodine-131 at a radiopharmacy connected to the treating institution or at a designated central radiopharmacy. At each clinical site, the ^{131}I -omburtamab dose should be assayed immediately prior to administration to verify that the prescribed activity and the activity actually administered agree within 10%. The residual activity in the dose syringe should then be assayed following administration to determine the net activity administered (= pre-administration activity – post-administration residual activity). The amount of radioactivity infused in patients should be assessed by measuring radioactivity of the infusion syringe before and after ^{131}I -omburtamab infusion into the indwelling intraventricular access device (e.g. Ommaya) and subtracting before and after counts. The radiolabeled ^{131}I -omburtamab is sterile filtered before administration. Patients will receive up to two cycles of ^{131}I -omburtamab.

7.1.1 Treatment

One ^{131}I -omburtamab cycle takes 4 weeks and includes a treatment dose followed by an observation period and post-treatment evaluations. The treatment dose is administered on day 1 of the first week in a cycle (according to **Table 1**). The patient will be followed for 4 weeks after the treatment dose. A full treatment is achieved when both cycles have been completed. Patients who finish both treatment cycles and complete week-8 assessments will enter the short-term follow up phase. Patients who finish only one treatment cycle will be registered as early treatment discontinuation and continue to the short-term follow-up visit at week 26. Please see Duration of treatment section 6.1.4.

7.2 Bleyer et al. 1977. Packaging and labelling of omburtamab

Packaging, labelling and release of omburtamab will be completed by KLIFO Supply in accordance with Good Manufacturing Practice (GMP) and national regulatory requirements. Label content will according to Annex 13, EudraLex, volume 4, local requirements and trial requirements. Each kit will be uniquely numbered.

7.2.1 Storage and handling

A description of IMP details is included in the IMP manual.

[figure not shown]
The Investigator or designee is responsible for ensuring that only eligible trial patients receive IMP. There is no storage of IMP at site, and the IMP is prepared on demand when a patient is found eligible for the trial and/or when subsequent cycles are being scheduled. The utensils used to ship, prepare and administer the IMP will be radioactive and should be destroyed according to local regulation. The destruction can be performed without sponsor approval. Drug accountability on a patient level is documented by keeping copies of the IMP Order Form, and the IMP Administration Form. The documentation will be reviewed periodically and verified by the CRA over the course of the trial.

7.2.2 Radiolabeling of omburtamab

Omburtamab will be radiolabeled with iodine-131 by a designated radio pharmacy following a qualified procedure outlined in a manufacturing agreement. Radiolabeling is performed by the iodogen method, which is based on previously published methods (Fraker and Speck 1978). Free iodine-131 is removed by ion exchange. Radiolabeled product will be pre-calibrated at the time of preparation to yield the prescribed activity at the projected time of administration as outlined in section 7.1. Radiolabeled product is sterilized by filtration to attain the target dose of 50 mCi, as applicable. Quality control is ensured according to a release specification, also including endotoxin testing, bioburden and radioimmunoassay.

7.2.3 Administration of ^{131}I -omburtamab

The radioactivity of the patient-specific unit doses must be within +/- 10 % of the intended dose (Table 4 Accepted activity ranges for treatment doses). Doses must be aseptically prepared by withdrawal of ^{131}I -omburtamab from the bulk vial into a sterile syringe. The finished product in liquid form is drawn into a syringe and then placed in a lead container (“pig”) that is then placed inside a lead lined container and transported to the patient’s bedside prior to administration. For detailed instructions, please refer to the IMP manual.

7.2.4 Radiation safety

Local safety instructions for storage and handling of radioactive IMP must be strictly followed. Radiation safety precautions may include patient isolation and the use of lead shielding, or designated rooms to ensure that the dose rate in the surrounding areas meets regulatory requirements.

Patients can be treated in an outpatient setting or may be admitted for ^{131}I -omburtamab administration. When patients are admitted, the caregiving staff will be instructed in radiation safety about steps required to minimize exposure to themselves according to local guidelines.

The dose rate from the patient will be measured after end of infusion and at later time points to define the need for overnight stay(s) using portable radiation detectors as described in the local

safety instructions. Patient release timepoint following administration of therapeutic amounts of ^{131}I -omburtamab will be determined based on the dose-rate criterion specified in Column 2 in table U.1 for ^{131}I in NUREG 1556, Vol 9, Rev 1 (US sites) or based on local radiation safety requirements (sites outside US). That is, patients can be released following administration of therapeutic amounts of ^{131}I -omburtamab if the dose rate measured with a survey meter at 1 meter from the patient does not exceed 7 mrem per hour or the value described by local safety instructions whichever is the lowest. Patient isolation will remain in effect until the dose rate is below what is required in accordance with local patient release regulations.

Patients and legal guardians must be advised of the risks of radiation exposure of household contacts, pregnant women, and small children and of the steps to be taken to reduce these risks. Legal guardians will be given instructions by radiation safety staff on how to handle waste and steps and procedures to follow to minimize exposure to themselves, household contacts, the general public and possible patient family caregiver(s). An evaluation of patient family caregiver doses will be performed, and appropriate radiation safety precautions will be taken to ensure that doses to these caregivers is maintained less than local requirements (e.g. 500 millirem or value determined by local safety instructions), in accordance with applicable regulations. Patients and/or caregiver will be provided with a written instruction detailing radio safety precautions as per the local requirements. The caregiver will agree to radiation safety instructions prior to administration of the therapeutic agent or the procedure may be delayed or declined.

The site's radiation safety service will manage the collection, shielding, and waste disposal, as appropriate, for patient excreta for each case. Following release of the patient, the site's radiation safety service will survey and perform decontamination procedures in the room to ensure that the room meets regulatory requirements.

